5.2. Effectiveness Analysis Set

The effectiveness analysis set (EAS) consists of all patients in the SAS except those who meet any of the following conditions:

- g. No effectiveness assessment has been reported (Indicated as "No effectiveness information" in the study report.)
 - The effectiveness assessments concerned include: Mayo stool frequency subscore, Mayo rectal bleeding subscore, Mayo findings of flexible sigmoidoscopy subscore, Mayo physician's global assessment of disease activity subscore, and faecal calprotectin.
- h. The disease of the patient is out of scope for this study (Indicated as "Out-of-scope disease" in the study report.)

The disease investigated in this study: Ulcerative colitis

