5. RATIONALE AND BACKGROUND

XELJANZ® Tablets 5 mg (non-proprietary name: tofacitinib citrate) (hereinafter "XELJANZ") is a potent inhibitor of Janus kinase (JAK) created by Pfizer Inc. In Japan, XELJANZ received marketing approval for the indication of "rheumatoid arthritis with inadequate response to existing therapy" in March 2013 and the indication of "induction and maintenance therapy for moderate or severe active ulcerative colitis (limited to cases with inadequate response to existing therapy)" in May 2018.

"XELJANZ® Tablets 5 mg Special Investigation (Investigation of Long-term Use in Patients with Ulcerative Colitis)" (hereinafter "Investigation") will be conducted based on the approval conditions in order to understand the safety and effectiveness of long-term use of XELJANZ in patients with ulcerative colitis in clinical settings. Information obtained in this study shall be used to report Ministry of Health, Labour and Welfare (MHLW), Pharmaceuticals and Medical Devices Agency (PMDA), and Pfizer Inc. which is the corporate parent of marketing authorization holder (or sponsor) of XELJANZ. And also, it shall be used for application of re-examination (including Japan Periodic Safety Report), re-evaluation, preparation of material for proper use information of XELJANZ, publications and activities for information service.

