7.2. Setting

7.2.1. Registration criteria

Patients must meet all of the following inclusion criteria to be eligible for inclusion in the study:

- Patients with ulcerative colitis treated with XELJANZ
- Patients naive to XELJANZ in the treatment of ulcerative colitis

For the "indications" and "dosage and administration" of XELJANZ, refer to the latest package insert of the drug.

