7.3.2. Pre-dosing observation

The following information should be recorded in CRF.

- 1. Height
- 2. . Body weight
- 3. Information on ulcerative colitis
 - a. Name of the disease
 - b. Date of diagnosis or duration of the disease
 - c. Extent of the lesion · (total colitis, left-sided colitis, proctitis, right-sided or segmental colitis)
 - d. Severity* (sever, moderate, mild; See Table 3.)

	rable 5. Classification of dicerative contributy sevenity				
	Severe	Moderate	Mild		
l) Frequency of stool	6 times or more	Intermed iate	4 times or less		

Table 3. Classification of ulcerative colitis by severity.

Xeljanz A3921248NON-INTERVENTIONAL STUDY PROTOCOL Version 5 (Amended 4). 17 December 2019

2) Obvious	(+++)	between severe	(+) to (-)	
bloody stool		and mild		
3) Fever	37.5°C or higher		(-)	
4) Tachycardia	90/min or more		(-)	
5) Anemia	Hb 10 g/dL or less		(-)	
6) Erythrocyte				
sedimentation	30 mm/h or more		Normal	
rate				
Note:				
• Rated as sev	ere when criteria 1), 2	2), and one of the syste	emic symptoms 3)	
alld 4) are s	atisfied, and at least 4	of the 6 criteria are sa	atisfied.	
• Rated as mil	d when all of the 6 cl	literia are satisfied.		
• Among patients with severe disease, those showing extremely severe symptoms are classified as having fululinant disease, and, depending on the				
rapidity of the disease onset. fuhninant disease is subdivided into acute				
fuhninant and relapsing fuhninant disease.				
• Patients satisfying all of the following 5 criteria are classified as having fulminant d isease.				

- 1. Satisfying the criteria for severe disease
- 2. Bloody diarrhea occurring at a frequency of 15 times/day or more
- 3. Persistent high fever (38°C or higher)
- 4. Increase of the leukocyte count to $10,000 \,/\text{mm}^3$ or more
- 5. Severe abdominal pa in

*: Criteria for diagnosis and treatment strategy for ulcerative colitis and Crohn's disease 2016 revised version (supplementary volume of the 2016 annual report of "Research Group of Intractable Inflammatory Bowel Disease" [Suzuki Group], Research on Policy Planning and Evaluation for Rare and Intractable Diseases, Health and Labom Sciences Research Grants)

- **: Patients with nlild disease ale not eligible for XELJANZ treatment.
- e. Status of refractory ulcera tive colitis based on treatment response (status of steroid dependency or resistance in the last episode before commencement of XELJANZ treatment)
- 4. Status of pregnancy (female patients only)

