7.6.4. Patient registration

7.6.4.1. Procedures for registration

Necessary information should be recorded in EDC registration form (patient registration screen), and patients should be registered at least 1 week before the commencement of XELJANZ treatment in principle.

If EDC is not available and when the PMDA has accepted to continuing the case registration only, information should be recorded in a paper registration form, and the form should be faxed to the Patient Registration Center at least 1 week before the commencement of XELJANZ treatment in principle.

In addition, as this investigation will be conducted with all patients surveillance system, all patients who are confirmed to be treated with XELJANZ should be registered.

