8.2.2. Patient characteristics and medical history

• Patient characteristics

Using the SAS (including subgroups by mean daily dose), set of patients treated for a long term (including subgroups by mean daily dose), and EAS, patients will be, according to the methods described in Section 8.1, summarized with respect to the following patient characteristics:

- Gender [male, female]
- Age (continuous)
- Age [<15 years, ≥15 to <65 years, ≥65 years]
- Age [<50 years, \ge 50 to <65 years, \ge 65 years]
- Body weight (continuous)
- Body weight [$<50 \text{ kg}, \ge 50 \text{ to } <60 \text{ kg}, \ge 60 \text{ to } <70 \text{ kg}, \ge 70 \text{ kg}$]
- BMI (continuous)
- BMI [<18.5, ≥ 18.5 to <25, ≥ 25]
- Diagnosis [ulcerative colitis, other]
- Duration of UC (continuous)
- Duration of UC [<2 years, ≥ 2 to <5 years, ≥ 5 to <10 years, ≥ 10 to <20 years, ≥ 20 years]
- Range of UC [pancolitis, left-sided disease, proctitis, right-sided or segmental disease, other]
- Severity of UC [mild, moderate, severe]
- Refractory UC based on treatment responsiveness [absent, present]
- Refractory UC based on treatment responsiveness [absent, steroid-resistant, steroid-dependent, present but not steroid-resistant or steroid-dependent]
- Past history [absent, present]
- Infections [absent, present]
- Past history of malignancy [absent, present]
- Past history of an autoimmune disease [absent, present]
- Past history of a cardiovascular disease [absent, present]
- Past history of lung disorder [absent, present]
- Past history of gastrointestinal disorder [absent, present]
- Past history of hepatic function disorder [absent, present]
- Hepatic function disorder: past history of hepatitis B [absent, present]
- Hepatic function disorder: past history of hepatitis C [absent, present]
- Hepatic function disorder: past history of hepatitis B virus carrier [absent, present]

- Hepatic function disorder: past history of hepatitis C virus carrier [absent, present]
- Past history of renal impairment [absent, present]
- Past history of metabolic abnormality [absent, present]
- Metabolic abnormality: past history of diabetes mellitus [absent, present]
- Past history of anaemia [absent, present]
- Complications [absent, present]
- Complication of an infection [absent, present]
- Complication of malignancy [absent, present]
- Complication of an autoimmune disease [absent, present]
- Complication of a cardiovascular disease [absent, present]
- Complication of lung disorder [absent, present]

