8.2.4.1. Effectiveness assessment based on the partial Mayo score

• Proportions of patients who achieved study endpoints based on the partial Mayo score

The proportion of patients who achieved each study endpoint based on the partial Mayo score (remission or clinical response) will be calculated with its 95% CI for each study visit. The definition of the study visits should follow "10.1. Appendix 1: Details of Data Handling".

The definition of the endpoints based on the partial Mayo score is shown in Table 1.

Table 1. Endpoints Based on the Partial Mayo Score

| Endpoint | Definition |
|----------------------|---|
| Remission based on | The patient is called to have achieved remission if they meet all the following criteria: |
| the partial Mayo | ● Partial Mayo score ≤2 |
| score | • Stool frequency subscore ≤1 |
| | • Rectal bleeding subscore ≤1 |
| | • Physician's global assessment subscore ≤1 |
| Clinical response | • The decrease from baseline in the partial Mayo score ≥2 |
| based on the partial | |
| Mayo score | |

• Changes in the partial Mayo score

Summary statistics will be presented for each study visit regarding the partial Mayo score and the change from baseline in the partial Mayo score. For the change from baseline, its 95% CI will also be presented. The definition of the study visits should follow "10.1. Appendix 1: Details of Data Handling".

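### The primary remission rate is not split by baseline status, so remission already present before the first dose is pooled with remission gained on treatment

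*SAP*

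**What the plan says.** **Who is in the set.** Protocol 7.2.1 registers "Patients with ulcerative colitis treated with XELJANZ" who have not had the drug for this disease before. Protocol 7.6.4.1 adds that "all patients who are confirmed to be treated with XELJANZ should be registered". The eligibility check on the registration form (Protocol 7.3.1) concerns contraindications. The exclusions from the safety set in SAP 5.1 are administrative. SAP 5.2 then states: "The effectiveness analysis set (EAS) consists of all patients in the SAS except those who meet any of the following conditions". One condition is the absence of any effectiveness data. The other is a disease outside the scope, defined by "The disease investigated in this study: Ulcerative colitis". No step sets a severity or baseline-score condition.

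**What is measured.** SAP 8.2.4 makes the partial Mayo remission proportion the primary effectiveness endpoint. In Table 1 of SAP 8.2.4.1, "The patient is called to have achieved remission if they meet all the following criteria": a partial Mayo score of 2 or less and each of the three subscores 1 or less. Baseline does not enter. Clinical response, in the same table, does use baseline: it needs a fall of at least 2 points.

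**What is split.** SAP 8.2.4.5 analyses remission at end of treatment in the effectiveness subgroups of SAP 5.4.2. Neither severity nor baseline score is among them.

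**Context.** Protocol 5 gives the indication as "induction and maintenance therapy for moderate or severe active ulcerative colitis (limited to cases with inadequate response to existing therapy". A note to Table 3 in Protocol 7.3.2 reads "Patients with nlild disease ale not eligible for XELJANZ treatment" (scan errors in the source text). SAP 8.2.2 lists "Severity of UC [mild, moderate, severe" among the characteristics to be tabulated.

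**The concern.** Table 1 speaks of remission being achieved, but its criteria describe only where the patient stands at a visit. In a set with no baseline condition, the proportion combines two quantities: remission reached by patients with active disease, and persistence of a state that existed before the first dose. The first is what a reader will take the result to mean, given the indication. As planned, the two cannot be separated in the primary result.

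The response rate has the opposite problem. Patients who start too low to lose 2 points can only count as non-responders, so they pull it down.

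This is the only primary effectiveness result, and the final analysis supports the re-examination application (SAP 3).

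**Working it through.** The plan gives no target or expected remission rate, and its sample size rests on herpes zoster, so there is no stated figure to reproduce. The check is a count of score combinations followed by a mixture calculation.

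**1. Combinations that already meet Table 1.** Three subscores, each 0 to 3, give 4 × 4 × 4 = 64 combinations. Requiring each subscore to be 1 or less leaves 2 × 2 × 2 = 8. Requiring a total of 2 or less removes (1,1,1), leaving 7. A patient at stool frequency 1, rectal bleeding 0, global assessment 1 before dosing, and unchanged afterwards, counts as a remission success at every visit with a score.

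**2. Combinations that cannot respond.** A fall of 2 needs a baseline total of at least 2. Totals of 0 or 1 arise in 1 + 3 = 4 combinations, all of them among the 7 above.

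These are counts of possible scores. They say nothing about how many patients have them.

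**3. Effect on the remission proportion.** Let f be the share of analysed patients already in Table 1 remission at baseline, q the share of those still in remission at the visit, and p the remission rate in patients not in remission at baseline.

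- Whole-set rate = (1 − f)p + fq
- Excess over p = f(q − p)

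The documents give none of f, q or p. Assumed ranges: f 5–20%, q 70–100%, p 30–60%. The smallest excess is at q = 70%, p = 60% (difference 10 points), the largest at q = 100%, p = 30% (difference 70 points).

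| Assumed f | Smallest excess | Largest excess |
|---|---|---|
| 5% | 0.05 × 10 = 0.5 points | 0.05 × 70 = 3.5 points |
| 10% | 0.10 × 10 = 1.0 points | 0.10 × 70 = 7.0 points |
| 20% | 0.20 × 10 = 2.0 points | 0.20 × 70 = 14.0 points |

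One case inside the range: f = 10%, p = 40%, q = 90% gives 0.9 × 40 + 0.1 × 90 = 36 + 9 = 45%, which is 5 points above p.

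For scale, the 95% confidence half-width 1.96 × √(p(1 − p)/470) is 4.1 points at p = 30%, 4.4 at 40% or 60%, and 4.5 at 50%. The 470 is the planned safety set. The effectiveness set cannot be larger than the safety set, and visit denominators may be smaller still.

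**4. Effect on the response proportion.** If g is the share with a baseline total of 0 or 1, and r the response rate among those who can respond, the reported rate is (1 − g)r. Because these 4 combinations lie within the 7, g is at most f among patients with a baseline score.

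**The case against.** **An all-patient set suits this study.** The approval condition asks for all treated patients. There is no comparator, and SAP 4.2 has no decision rule. Remission among everyone treated is a legitimate descriptive quantity. This stands, and it is why the whole-set figure should stay.

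**Other planned tables partly reveal the problem.** SAP 8.2.2 tabulates each baseline subscore as 0, 1, 2 or 3, baseline Mayo below 6 or not, and severity, for the effectiveness set as well. The smallest of the three shares scoring 1 or less is an upper bound on the share in remission among patients with baseline scores. SAP 8.2.4.1 and 8.2.4.3 add changes from baseline. Appendix 1 lists baseline as a visit, so a baseline remission proportion might even be printed. This stands in part: none of these outputs separates later remission by baseline status.

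**The share may be very small.** The stated indication is active disease after inadequate response to other therapy, and no passage shows that any patient starts in remission. This stands as a limit on size.

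**A stronger reading is tempting.** A reader might infer that, since the protocol calls mild disease ineligible while the SAP lists a mild category, the plan expects mild patients and will count them as remissions. The documents do not support this. Mild in Table 3 uses daily stool count, visible blood, fever, pulse, anaemia and sedimentation rate; it is not the partial Mayo score. A patient with 4 stools a day whose normal is 1 has 3 more than normal, scores 2 for stool frequency and fails Table 1, yet meets the mild stool criterion. The note concerns eligibility for treatment, not membership of an analysis set. Nor does a listed category show that such patients are expected: the same list keeps a diagnosis other than ulcerative colitis, which SAP 5.2 removes from the effectiveness set.

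**Replacing the primary denominator would carry its own problems.** The partial Mayo baseline window reaches back 6 months (SAP Appendix 1), so an old score could misclassify a patient who was active on Day 1. Patients without a baseline score would drop out. Protocol 7.7.2.2 sends major changes to primary endpoint analyses to a protocol amendment, and SAP 4.0 (30 May 2022) postdates the planned end of data collection (June 2021). This stands, and argues for adding a split and leaving the primary figure in place.

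**Conclusion.** The point holds as a gap in how the primary effectiveness result is presented. Nothing from registration to the effectiveness set imposes a baseline condition, Table 1 remission is an absolute state, and no planned effectiveness analysis separates patients by whether they already met it. Remission gained and remission retained are therefore pooled, and patients who cannot respond are not taken out of the response denominator.

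The direction is upward for remission whenever q exceeds p. The size is unknown: 0.5 to 14 points over the assumed ranges, and close to nothing if few patients start in remission. A statement that the reported rate is overstated by a particular amount would go beyond the documents. The mild-disease note is supporting context only; the argument rests on the missing baseline split.

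**What to change.** Keep the whole-set remission proportion as the stated primary figure. Add the following to the SAP:

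- **SAP 8.2.4.1 and 8.2.4.5, remission.** Beside the whole-set figure, give the proportion with its 95% CI in three rows: not in Table 1 remission at baseline, already in remission at baseline, and baseline score missing. State that conclusions about achieving remission rest on the first row.
- **SAP 8.2.4.1, clinical response.** Calculate it among patients with a baseline partial Mayo score of at least 2, and give the number with a score of 0 or 1 separately.
- **Baseline timing.** Report how long before Day 1 the baseline score was recorded, because the window extends to 6 months.

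The data are already collected, and eligibility and treatment are untouched. The cost is SAP wording and extra table rows. The baseline-active row will have a smaller denominator and a wider interval, by an amount that depends on how many baseline scores are missing, and old scores may place some patients in the wrong row. Because the primary figure is kept, the amendment clause in Protocol 7.7.2.2 is less likely to be engaged than if the denominator were replaced.

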5.3. Other Analysis Sets

Not applicable.

5.4. Subgroups

5.4.1. Subgroups by dose level

The following subgroups will be defined depending on the mean daily dose to evaluate the safety of this drug and the dose response of the safety in patients treated mainly at 10 mg BID:

• Subgroups by mean daily dose (patients treated mainly at 10 mg BID, patients treated at a higher dose level, patients treated at a lower dose level)

Among the patients in the SAS, those who were treated at a mean daily dose of 17 mg or higher will be defined as patients treated mainly at 10 mg BID.

Among the patients in the SAS, those who were treated at a mean daily dose of 15 mg or higher will be defined as patients treated at a higher dose level; similarly, those who were treated at a mean daily dose of <15 mg will be defined as patients treated at a lower dose level.

The mean daily dose should be calculated as:

Mean daily dose = (Total dose administered during the treatment period) / (Total number of days in the treatment period including non-dosing days)

• Patients treated for a long term

Among the patients in the SAS, those with a duration of treatment of >16 weeks are defined as patients treated for a long term.

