All adverse events (AEs) occurring from the start of treatment to the end of the observation period will be collected for patients whose observation period is 60 weeks or less. For patients whose observation period exceeds 60 weeks, all AEs will be collected until 60 weeks and thereafter only malignancies and AEs leading to discontinuation of treatment will be collected.

• Analysis for safety evaluation

In the safety analysis set, the onset of major adverse reactions (AEs considered by the physician to be related to this drug), incidence of adverse reactions (number/percentage of patients with adverse reactions), and incidence of adverse events per duration of exposure (100 × number of patients with adverse reactions / total duration of exposure / 100 person-years) will be set as primary analysis items. In addition, factors that may affect the onset of adverse reactions will also be examined by conducting subgroup analyses based on patient background and other factors.

• Analysis for effectiveness evaluation

In the effectiveness analysis set, the rate of remission based on partial Mayo score will be set as primary analysis items.

• Dosage and administration of this drug

For induction, the recommended dose of this drug is 10 mg administered twice daily (10 mg BID [bis in die]) for 8 weeks. If the response is inadequate after the 8 weeks course of treatment, another 8 weeks course may be administered.

For maintenance, the recommended dose is 5 mg twice daily (5 mg BID). If the response decreases during the maintenance, the dose level may be increased to 10 mg BID. Intractable patients for whom prior drug therapies (e.g., a TNF inhibitor) were ineffective may be treated with 10 mg BID.

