 - Duration of treatment >45 to ≤ 60 weeks
 - Duration of treatment >60 to ≤ 75 weeks
 - Duration of treatment >75 to ≤90 weeks

• Duration of treatment >90 to <105 weeks

- Duration of treatment >105 to <120 weeks
- Duration of treatment >120 to ≤135 weeks
- Duration of treatment >135 weeks

The duration of treatment is defined as the period from the start date of the treatment with this drug to the last observed administration date of this drug, including non-dosing days.

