8.2.3. Safety analyses

Adverse reactions or AEs included in a summarization will be those that developed from the start of treatment to the end of the observation period or 60 weeks after the start of treatment, whichever came first, except for malignancy, for which all events occurring by the end of observation period will be included in a summarization. All adverse reactions and AEs reported in this study will be included in a listing.

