To evaluate the dose-response relationship concerning the safety of the treatment with this drug, the following analyses will be performed in the patients treated at a higher dose level defined in Section 5.4.1 and in the patients treated at a lower dose level. To eliminate the effect of including patients who discontinued treatment during the induction phase, similar analyses will also be performed in patients treated at a higher dose level for a long term and in patients treated at a lower dose level for a long term:

• Adverse reactions of each element in the safety specification will be summarized in terms of number and proportion of patients as well as incidence and its 95% CI. In addition, the risk ratio and risk difference with their 95% CI will be presented for the patients treated at a higher dose level compared with those at a lower dose level.

• Adverse reactions will be summarized by SOC and PT in terms of number and proportion of patients.

In addition, to investigate the temporal change in the risk of the occurrence of each event, the following analyses will be performed in the patients treated at a higher dose level and patients treated at a lower dose level:

[figure not shown]
- Patients who experienced adverse reactions of each element in the safety specification will be summarized by timing of first onset, in terms of n and proportion as well as incidence and its 95% CI. As for the denominator to calculate the proportion, the denominator to calculate the incidence, and the categories used for onset timing, the corresponding descriptions in (1) should be followed.
- A Kaplan-Meier plot will be presented for the time to first onset of any adverse reaction included in each element in the safety specification.

• Subgroup analyses regarding patient characteristics

According to Section 8.1.3, the risk ratio based on the proportion of patients who experienced adverse reactions of each element in the safety specification will be determined and graphically presented for different subgroups regarding each of the patient factors defined in Section 8.2.2 in which events developed in ≥ 10 patients. Risk ratios will not be calculated for subgroups in which events developed in < 10 patients.

For each relevant subgroup defined in Section 5.4.2, patients who experienced adverse reactions will be summarized by SOC and PT in terms of n and proportion.

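### Dose groups built on whole-course mean daily dose depend on treatment duration and on later dosing, so the higher-versus-lower comparison cannot be read as dose response

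*SAP*

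**What the plan says.** SAP 5.4.1 divides the total dose by the "Total number of days in the treatment period including non-dosing days". Those "treated at a mean daily dose of 15 mg or higher will be defined as patients treated at a higher dose level"; patients below 15 mg form the lower group, and those at 17 mg or more are labelled as treated mainly at 10 mg BID. SAP 8.2.2 runs the duration of treatment from the first dose "to the last observed administration date of this drug, including non-dosing days", with categories beyond 135 weeks. Under SAP 8.2.3, events count until the end of observation or "60 weeks after the start of treatment, whichever came first, except for malignancy".

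SAP 8.2.3.3(2) has dose response as its stated purpose. There, "the risk ratio and risk difference with their 95% CI will be presented for the patients treated at a higher dose level" against the lower group, together with incidence, onset by period and Kaplan-Meier plots for the same groups. The analyses are repeated in patients treated for more than 16 weeks, "To eliminate the effect of including patients who discontinued treatment during the induction phase".

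On dosing, SAP 2.1 states: "For induction, the recommended dose of this drug is 10 mg administered twice daily" for 8 weeks. It allows a second 8-week course and describes 5 mg BID for maintenance. It adds: "If the response decreases during the maintenance, the dose level may be increased to 10 mg BID". Some refractory patients may also be treated at 10 mg BID.

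**The concern.** A dose-response comparison needs an exposure that is settled before the outcome. This one is known only when treatment ends, and four things feed into it besides the dose at risk:

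1. **Duration.** Patients on one and the same regimen are split by how long they stayed on it.
2. **Dosing after the event.** SAP 8.2.3.1 lists discontinuation, interruption or reduction, and increase as actions taken after a reaction. Each changes the mean, so the outcome helps to decide the exposure group.
3. **Dosing after Week 60.** It can move a patient between groups although no event other than malignancy counts by then.
4. **Non-dosing days.** They lower the mean. This matters mainly where the interruption follows an event.

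The SAP respects the principle elsewhere. The concomitant-drug analyses in 8.2.3.1 and 8.2.3.2 drop drugs used after the first onset, and 8.1.4 ends exposure time at the first event. At stake is the SAP's only higher-versus-lower dose comparison, which could suggest harm or reassurance where there is neither.

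**Working it through.** The documents give no figure for this comparison, so there is none to reproduce. The classification below is exact arithmetic from SAP 2.1 and 5.4.1.

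**Duration.** With k weeks at 20 mg/day and then 10 mg/day until Week T, the mean is 10 + 10k/T.
- At least 15 mg requires T ≤ 2k: Week 16 for k = 8, Week 32 for k = 16.
- At least 17 mg requires T ≤ 10k/7: Week 11.4 or Week 22.9.

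**After the event.** An event at Week 20 on 20 mg/day, then 10 mg/day to Week 60, gives (20×20 + 40×10)/60 = 13.3 mg: lower group. Stopping at the event gives 20 mg: higher group.

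**After Week 60.**
- 20 mg/day to Week 40, then 10 mg/day: (40×20 + 20×10)/60 = 16.7 mg at Week 60, but (40×20 + 60×10)/100 = 14.0 mg at Week 100.
- The reverse, 8 weeks at 20, 52 at 10, then 70 at 20 mg/day: (8×20 + 52×10)/60 = 11.3 mg at Week 60, but (8×20 + 52×10 + 70×20)/130 = 16.0 mg at Week 130.

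**Non-dosing days.** On 20 mg/day with a share x of days without dosing, 20(1 − x) < 15 when x > 25%.

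**Simulation.** The event rate of 8/100 PY comes from the sample-size rationale; every other input is assumed: extended induction 30 or 60%; kept on 10 mg BID 10 or 30%; later escalation 0, 15 or 30/100 PY; other discontinuation 45/100 PY. That makes 12 scenarios per row with 400,000 patients each, and treatment capped at Week 60. With **no dose effect**:

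| How dosing responds to events | All-patient risk ratio |
|---|---|
| None stop; half of those on 20 mg/day lead to reduction | 0.3–0.5 |
| No response | 0.5–0.8 |
| Mixed: 25–50% stop; 25–50% of the remaining events on 20 mg/day lead to reduction | 0.7–1.3 |
| Every event stops treatment | 1.7–2.8 |

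- *Mixed case, all patients:* risk difference −2.9 to +1.7 points, incidence ratio 0.9–2.8.
- *Mixed case, >16-week set:* risk ratio 0.7–1.2, incidence ratio 0.7–1.6.
- *Sensitivity:* other discontinuation of 25 or 90/100 PY moves the mixed risk ratio to 0.74–1.67 or 0.50–0.87. With 10% of patients starting at 10 mg/day it is 0.68–1.25.
- *Treatment past Week 60 (ending uniformly in Weeks 60–150):* mixed risk ratio 0.6–1.3; up to 7% of patients treated beyond Week 60 change group because of later dosing.

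A second simulation with other assumed inputs (30% extended induction, 0–25% kept on 20 mg/day, 0–60% of events changing treatment, discontinuation 2% per week to Week 16 and 0.8% after) gave risk ratios with no dose effect of 0.17–0.93 in all patients and 0.42–1.84 in the >16-week set.

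**True rate ratio 2** (6/100 PY on 10 mg/day, 12 on 20 mg/day), mixed case: the planned risk ratio is 0.9–1.8 in all patients and 0.95–1.6 in the >16-week set. Splitting person-time by current dose within >8–16 and >16–60 weeks gives 1.95–2.10 (0.96–1.05 when there is no effect).

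**Incidence in the >16-week set** (truth 8/100 PY), when 0, 25, 50 or 100% of events stop treatment: 8.0, 7.4, 6.7, 5.5. The set keeps the first 16 weeks of person-time but drops patients whose event ended treatment by then. Counting events and time from Week 16 gives 7.9–8.1.

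**The case against.** The comparison is descriptive: SAP 4.2 has no decision rules, and the primary safety items use the whole safety set. At N = 470 the planned risk ratio has a 95% CI factor of about 1.9–2.3, so the mixed-case bias in it lies within sampling error for one event type. All of that stands and limits the severity. The incidence-ratio bias (up to 2.8) can exceed that factor, although the SAP prints incidences rather than their ratio.

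The SAP also foresaw part of the problem. For 8-week induction followed by 5 mg BID, the 15 mg crossing is exactly Week 16, so the >16-week repeat removes the duration effect. If dosing does not react to events, the incidence ratio is 0.95–1.07 in all patients and 0.95–1.05 in the >16-week set, so duration alone biases the risk ratio and risk difference but not the incidences. That is correct, but extended induction, later escalation and event-driven dosing remain. The tables of mean dose by duration and of discontinuation by dose group (SAP 8.2.1, 8.2.2) show the dependence without correcting the ratio.

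Two of the four routes are weak. SAP 5.4.1 does not itself define the treatment period, so the Week 60 point relies on the definition in 8.2.2; its effect is small and it does not apply to malignancy. A patient with many non-dosing days did receive a lower average dose.

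Finally, the current-dose split recovers the truth in a simulation whose events were generated from current dose. That shows the method is consistent with that model, not that the model is right.

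**Conclusion.** The point holds and should be fixed. That the grouping depends on duration, on dosing after the event and on dosing after Week 60 follows from the SAP's definitions and needs no assumption. With no dose effect the risk ratio can fall on either side of 1, and a real doubling can look like no difference. Direction and size cannot be predicted, because the documents do not say how often events lead to stopping or reduction; the simulated ranges are illustrations, not bounds. The 17 mg group has the same defect. Primary analyses are not affected.

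**What to change.** Using the dose record in Protocol 7.3.3:

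- Add an analysis that splits person-time by the dose in force, assigns each first event to the dose at onset, and reports incidence per 100 PY with a rate ratio stratified by time since start. Stratification is essential: with a higher early hazard (16 before and 6/100 PY after Week 16) and no dose effect, current dose alone gave 1.65, against 1.02 after Week 16.
- Use only time strata in which both dose levels have person-time. The first 8 weeks qualify only if enough patients start below 20 mg/day.
- In the >16-week set, count events and person-time from Week 16 and apply the same split.
- Keep the mean-dose tables as description, without the risk ratio, the risk difference or the dose-response label, and state that they include dosing after the event and after Week 60.
- For malignancy and other long-latency events, give descriptive tables only. Dose at onset is not a suitable exposure there, and cumulative dose grows with follow-up.
- State that confounding by severity remains.

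**Cost.** SAP wording and programming; no new data. SAP 4.0 is dated after the planned end of data collection, so the addition should be labelled as such. Precision is low: at the zoster rate, about 4–12 events fall on 20 mg/day and 15–23 on 10 mg/day after Week 8. The CI factor exp(1.96√(1/e20 + 1/e10)) is 2.9 for 4.0 and 22.9 events and 2.1 for 12.3 and 14.6. Section 8.2.3.3(2) counts only reactions judged related, so there may be fewer. At 1/100 PY only 0.5–1.5 events would fall on 20 mg/day, and the ratio is close to uninformative. If patients with extended induction or kept on 10 mg BID have a 1.5-fold rate for reasons other than dose, the current-dose ratio is 1.15–1.35 with no dose effect.
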